6.9 Will non-English speakers will be enrolled in the study? Yes No

No

If yes, confirm what language will be used to consent prospective study participants. If the language used to consent is not the same language used by study participants or their legally authorized representatives, describe what methods and materials will be used to confirm their understanding of the study:

7 STUDY PROCEDURES

7.1 Study visits including procedures/tests involved (e.g., blood test, x-rays, questionnaires. If numerous study visits and procedures are involved, include a study procedure timeline):

The participant's Housing Site will be assigned by random, such as the flip of a coin, to participate in either a Tai Chi or Health and Wellness Activity study group. The participant will be asked to take part in whatever group his/her housing site has been assigned. Participants in the Tai Chi Activity group will be asked to attend for one hour twice a week for twelve months, or a total of 96 classes. Participants in the Health and Wellness Activity group will be asked to attend for one hour, once a month for a total of 12 classes.

Study Groups: The Tai Chi study group will be led by a certified Tai Chi instructor. It will consist of warm-up exercises, stretches, and Tai Chi movements developed for use with older adults. The participant will be asked to attend all of the classes in the assigned study group over the one year period. He/She may also be asked to watch and follow along with a Tai Chi instructional video in his/her apartment at his/her convenience one or two times each week for 15-30 minutes. If he/she does not have a video player, one will be provided

to use during your study enrollment. The video will consist of warm-ups, seated stretches, and simplified Tai Chi movements. The participant will be asked to keep a log of practice dates and times and bring this to class with them for review with the instructor, and will be regularly collected. The Health and Wellness Activity study group will also be led by a trained instructor. Activities will include lectures and discussions on healthcare topics of interest to older adults. All sessions will take place in a common room of the housing facility. The instructors will have access to water for participants and a phone in case of emergency. **PARTICIPANTS WHO ENROLLED IN WAVE 2, PAIR 3 WILL NOT TAKE PART IN EITHER OF THE STUDY INTERVENTIONS.**

Assessments: Participants will be asked to complete an assessment described below on 3 separate occasions. The first assessment will occur before beginning the assigned activity group of either Tai Chi exercise sessions or Health and Wellness sessions, twice a week for one year. The second assessment will occur six months (+/- 3 weeks) after beginning the sessions and the third assessment will occur twelve months (+/- 3 weeks) after beginning the sessions. (Wave 2, participants from Housing site pairs 1 and 2, participation will end following the second assessment at six months. These participants will not be asked to complete a third assessment at twelve months. This is due to the recent decision by the NIA and DSMB to stop the study intervention at this time. Only these Wave 2 site pairs will have reached the point of the six month assessment at the time that the study intervention is stopped.) It will take about two hours to complete each of these three assessments. A trained research assistant will carry out the assessments which will take place in the participant's apartment or a private place at the housing facility.

1. **Health Interview** - At each of the three assessments, the participant will be asked questions about his/her health, medications, history of falls, whether he/she has had any hospitalizations or emergency room visits. Height, weight, blood pressure and heart rate will be measured. Participants will be asked questions about daily activities, mood, sleep, memory and balance.

2. **Balance and Walking Test** - Participants will be asked to perform several activities such as walk a few yards, stand up from a chair, and stand with one foot beside or in front of the other. Participants will also be asked to walk at his/her own pace several times in a quiet hallway while a trained research assistant walks with him/her for safety. Participants will be asked to wear small wireless accelerometers, the size of a wristwatch (Mobility Labs™) to capture gait, walking and balance data. The monitors will be placed at the ankles and the waist, and attach quickly and easily like a wristwatch with a velcro strap. During one of the walking trials, the participant will be asked to count out loud while they are walking. Participants will be able to rest if needed during the test, and a chair will be available to sit down if he/she becomes tired. He/She will be asked to stand for one minute, up to six times. During two of the one minute stands the participant will be asked to count out loud. The wireless accelerometers will measure how much he/she sways as he/she are standing still. An experienced research assistant will be at his/her side at all times to ensure safety during all balance tests. Participants will be able to rest as needed.

3. Handgrip strength - Participants will be asked to squeeze a handgrip device with his/her dominant hand three times. Participants will rest between each trial. The handgrip device will measure strength in the handgrip and forearm.

Pilot Testing: Prior to the start of data collection at the housing sites, we will pilot test the above procedures, that is, the Health Interview, the Balance and Walking Tests, and the Handgrip strength test. The purpose of the pilot testing is to train and certify the Research Assistants in the study procedures, to assure inter-rater reliability among RAs, and initially to refine the order of the study procedures for maximum efficiency. We will ask up to 20 volunteers to complete the pilot testing each year as needed to recertify staff or train newly hired staff in the study procedures. Pilot study volunteers will not be potential study participants.

Monthly Phone Calls – A research assistant will call participants each month to check in with the participant and to ask about any falls, hospitalizations or emergency room visits. If the participant has a fall at any time over the course of the year that he/she is participating in the study, he/she will be asked a few questions about the fall, such as where he/she was and what he/she was doing at the time of the fall. Health Care Service Utilization – Participants will be asked to provide his/her Medicare Unique Patient Identifier Number. In order to determine whether taking part in Tai Chi or Health and Wellness activities regularly for one year has any impact on needed health care services, such as doctor's visits, hospitalizations or emergency room visits, we will request permission to track the participant's Health Care Service Utilization encounters over the course of the year that he/she are taking part in his/her assigned activity group and for one year following the completion of his/her assigned activity group.

After the participants verbally consent to participate in the focus group, the focus group leader will use a discussion guide developed by the research team to explore how participants feel over these time periods, their motivation, social connections, sense of social support, satisfaction with the instructor, affect, and willingness to continue. For the drop-outs, the leader will also explore reasons for not participating. The discussion will be recorded and key themes will later be extracted using the qualitative procedure described below. These themes will be described in a publication and used to develop methods to promote adherence in future exercise interventions.

Through an iterative process, we will use the immersion/crystallization technique to analyze the transcripts for themes. After each group session, the leader will summarize their impressions of the discussion and its major themes. All of the investigators will review each of the transcripts independently and develop coding categories to describe important segments. We will not restrict categories to those targeted by the discussion guide; each reviewer will develop categories from the content of the transcripts. Second, we will hold a series of meetings to review each transcript together, discussing our different codes until we reach consensus. Finally, one investigator will review all coded segments, group them into themes, and identify quotations that illustrate the themes.

7.2 List procedures being performed as routine medical care (e.g. for diagnostic or treatment purposes):

None of the procedures described above are being performed as routine medical care.

7.3 List procedures being performed solely for the research:
All the procedures described in section 7.1 are being performed solely for the research.

7.4 Describe the methods used to protect participant privacy:
All study interviews will be conducted in a private space, either in the participant's apartment or a private area of the housing site.

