6.5	
Participant recruitment (describe recruitment methods and submit any materials to be used to recruit participants): This study calls for recruiting 320 elderly individuals living in 16 subsidized senior housing facilities. The facility managers have all agreed to cooperate with this study, provide us with access to their residents, inform them about the study, and encourage participation. In addition, we will post information promoting the study, conduct public information sessions in each facility, place notices in all resident mailboxes and newsletters, and inform residents that they will be visited personally by research staff. We have contracted with the Center for Survey Research of the University of Massachusetts-Boston (CSR) to conduct door-to-door recruitment by having trained interviewers speak directly with potential study participants. CSR has experienced interviewers who are themselves older adults and can relate to and establish trust from older adult populations. Using similar door-to-door recruiting, CSR helped us recruit 765 seniors > 70 years of age from the local Boston metropolitan area for the MOBILIZE Boston study between 2006-2008.
 
Subjects will be recruited and studied in 2 waves. Recruitment will occur during the first 6 months of each wave. If a resident agrees to participate, the recruiter will conduct a brief screen for inclusion and exclusion criteria. If the volunteer passes the screen, their baseline assessment will be scheduled as soon as possible.
 
WE WILL INTRODUCE THE FOCUS GROUP DURING THE REGULAR SESSION FIRST. WE WILL THEN SEND OUT AN INTRODUCTORY MAIL FOLLOWED BY A PHONE INVITATION TO RECRUIT THE PARTICIPANTS.
 
FOR THOSE WITHDRAWAL FROM THE CLASS, WE WILL SEND OUT AN INTRODUCTORY MAIL FOLLOWED BY A PHONE INVITATION TO RECRUIT THE DROP-OUTS.
		

RECRUITMENT FOR THE STUDY IS NOW DISCONTINUED, AS DETERMINED BY THE NIA, FOLLOWING THE DSMB MEETING AND FOLLOW UP DISCUSSIONS OF 10/25/17.

6.6 Procedures for obtaining informed consent, including who will obtain consent and the timing of consent from recruitment:

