PARTICIPANTS WHO HAVE BEEN ENROLLED IN WAVE 2, PAIR 3, WILL BE WITHDRAWN FROM THE STUDY, DUE TO THE DECISION OF THE NIA TO STOP THE TRIAL. THESE PARTICIPANTS HAVE COMPLETED A BASELINE ASSESSMENT BUT WERE NEVER ENROLLED IN THE STUDY INTERVENTION. A LETTER OF EXPLANATION TO BE SENT TO THESE PARTICIPANTS IS ATTACHED. FOR PARTICIPANTS ENROLLED IN WAVE 2, PAIRS 1 AND 2, IN WHICH THE INTERVENTIONS WERE UNDERWAY, THE INTERVENTIONS WILL BE STOPPED, AND PARTICIPANTS WILL RECEIVE A LETTER OF EXPLANATION, ATTACHED.

6.8 If the participants may have diminished capacity to provide informed consent or to understand study procedures (now or in the foreseeable future), describe additional safeguards to protect their rights and welfare, including how and when you will engage legally authorized representatives:

Only participants capable of providing individual consent will be enrolled in the study. To be sure the subject is capable of providing informed consent, we will briefly screen volunteers for their cognitive capacity before enrolling them and will accept those who can recall at least 2 of 3 words in 3 minutes and 2 of 3 key elements of the study protocol. For participants with little or no formal education we will read the informed consent form with a family member present if the participant wishes, and an appropriate witness (the housing sites have a care advisor/social services advisor on site who can serve as the witness) . For individuals with little or no formal education, we will ask participants to answer the following questions to assess their understanding and assure they are informed.

1. Can you tell me in your own words what this study is about, and what is involved if you participate? 2. Is the study voluntary or do you have to participate? If you choose to participate, do you have to stay in the study until it ends or can you withdraw whenever you would like or need to? 3. Are there any benefits to you for participating in the study? (If yes, can you explain the benefits?) Are there any risks to you for participating in the study? (If yes, can you explain the risks?) 4. Have you had enough time to make your decision to participate? 5. Do you have any questions about the study? 6. Please explain how you will contact the study staff if you have any questions or problems during the study.

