8 STATISTICAL PLAN

8.1 Statistical methods:

Analysis for each Aim: Specific Aim 1: To determine the effects of the Tai Chi intervention on functional performance over a one-year period in poor, multiethnic, elderly residents of subsidized housing facilities. The primary functional outcome will be the Short Physical Performance Battery (SPPB) score. We will also examine the effects of Tai Chi on self-reported physical and mental health, gait and balance, falls, executive function, social engagement, overall activity level, and other patient-centered outcomes.

The effect of the Tai Chi intervention on functional performance as measured by SPPB will be estimated from a shared-baseline linear mixed model with fixed effects for age, follow-up time, age x time interaction, and treatment x time interaction and random effects of community, site within community, participant within site, community x treatment, community x time, community x treatment x time, site x time, and participant x time interactions. The shared baseline across treatment groups reflects homogeneity of the population with respect to treatment prior to random assignment and adjusts for effects of baseline level in a manner equivalent to ANCOVA. The random effects acknowledge the expected correlations among sites within a community, among participants within a site, and among repeated longitudinal assessments of each participant. This approach also naturally accommodates unequal enrollment across sites and loss to follow-up, even potentially informative loss to follow-up, if well predicted by the observed data on participants prior to drop-out. All participants will be included in the primary analysis according to their treatment assignment, following the intention-to-treat principle. Primary inference will be based on a two-tailed test at alpha = 0.023 of the fixed treatment x time interaction estimating Tai Chi-dependent improvement in rates of change in SPPB. An additional alpha = 0.002 is reserved for one interim analysis. The total two-tailed alpha = 0.025 for testing SPPB preserves an overall type I error rate of 0.05 for the functional and utilization primary aims. In addition to intention-to-treat analyses, we will perform secondary per-protocol analyses, defining participants in a tai chi group as 'per-protocol' if they attended ≥50% of tai chi classes averaged over the year-long intervention.

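### The Aim 1 SPPB model has no wave term, although since the stop wave alone decides who can have a 12-month SPPB value

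*Combined protocol and SAP*

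**What the plan says.** Section 6.5 states "Subjects will be recruited and studied in 2 waves". Sections 6.7 and 7.1 then refer to wave 2 sites by pair number, and the stop was carried out pair by pair:

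- Section 6.7, pairs 1 and 2: "FOR PARTICIPANTS ENROLLED IN WAVE 2, PAIRS 1 AND 2, IN WHICH THE INTERVENTIONS WERE UNDERWAY", those interventions are halted. Section 7.1 adds that "Wave 2, participants from Housing site pairs 1 and 2, participation will end following the second assessment at six months" and that "These participants will not be asked to complete a third assessment at twelve months".
- Section 6.7, pair 3: "PARTICIPANTS WHO HAVE BEEN ENROLLED IN WAVE 2, PAIR 3, WILL BE WITHDRAWN FROM THE STUDY". These participants had a baseline assessment and no intervention.
- Section 8.1, interim analysis: the futility decision used 12-month data from wave 1.

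Allocation is described in section 7.1 only as "The participant's Housing Site will be assigned by random, such as the flip of a coin". No section says how pairs were formed, whether each pair had one site per arm, or whether allocation was stratified by wave.

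The Aim 1 model in section 8.1 has "fixed effects for age, follow-up time, age x time interaction, and treatment x time interaction". Its random part begins with "random effects of community, site within community, participant within site, community x treatment, community x time" and goes on to further community, site and participant interactions with time. Wave and pair are absent. The same section keeps all participants in the primary analysis and relies on the mixed model to handle loss to follow-up that the observed data predict. It does not say how the shortened wave 2 follow-up enters the final analysis.

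**The concern.** The mixed model's protection against missing follow-up depends on the reasons for missingness being captured by what is modelled. Here the largest block of missing 12-month values was created by an administrative decision that follows wave exactly, and wave is not in the model. Two problems follow.

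1. If the waves differ in their rate of SPPB change and the arms are unequal within waves, part of the wave difference is credited to treatment.
2. A single linear slope treats a six-month-only site as informative about month 12 by doubling its six-month effect. If the effect levels off early or starts late, the pooled slope no longer estimates the 12-month difference on which the sample size was based.

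The pair labels raise a separate question. If sites were matched and randomized one per arm, an analysis without pair uses a standard error that does not reflect the matching.

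**Working it through.** **Inputs from the documents.** Pilot standard error 0.268 at 3 months with 2 sites; 16 sites of about 20; two-sided alpha 0.023; 85% power for 1.38 points (section 8.2). Wave and pair follow-up as in sections 6.7 and 7.1.

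**Inputs assumed because the documents do not give them.** Eight pairs in all (16/2); three of them in wave 2, leaving 8 - 3 = 5 in wave 1; the variance components; a wave slope difference of 0.8 points/year; and the within-pair correlation rho of site-level change.

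**Step 1: the plan's own power.** SE = 0.268 x 12/3 x sqrt(2/16) = 0.379. A noncentral t with 16 - 2 = 14 degrees of freedom gives 84.7% power at 1.38, which matches the stated 85%. A normal approximation gives 91.4% and does not match. The stated power thus corresponds to an unpaired site-level test with nothing spent on wave or pair.

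**Step 2: the SPPB data after the stop.**

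| Group | Baseline | 6 months | 12 months |
|---|---|---|---|
| Wave 1 | yes | yes | yes |
| Wave 2, pairs 1 and 2 | yes | yes | no |
| Wave 2, pair 3 | yes | no | no |

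**Step 3: wave differences.** The model was simulated with 5 wave 1 pairs and 2 wave 2 pairs, and a wave slope difference of 0.8 points/year.

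- Arms balanced within wave: bias in treatment x time about 0.
- One site swapped, so that arms are unequal across waves: bias about 0.15 points/year (0.148).
- The same imbalance with wave and wave x time added: bias -0.001.

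**Step 4: non-linear effect, arms balanced, true 12-month effect 1.38.**

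| True pattern | All data | Wave 1 only |
|---|---|---|
| Full effect already at 6 months | 1.66 | 1.42 |
| No effect until after 6 months | 1.10 | 1.33 |

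The cause can be read off the table. Let d6 and d12 be the true effects at 6 and 12 months.

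- In the late pattern d6 = 0, so the weight on d12 is 1.10/1.38 = 0.80 with all data and 1.33/1.38 = 0.96 with wave 1 only.
- In the early pattern d6 = d12, so the two weights sum to 1.66/1.38 = 1.20 with all data and 1.42/1.38 = 1.03 with wave 1 only.
- The weight on d6 is therefore 1.20 - 0.80 = 0.40 with all data, against 1.03 - 0.96 = 0.07 with wave 1 only.

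The pooled slope is about 0.40 d6 + 0.80 d12. It equals d12 only when d6 is half of d12.

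**Step 5: cost of the wave terms.** One site-level degree of freedom fewer (13 instead of 14, same SE) moves power at 1.38 from 84.7% to 84.0%.

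**Step 6: pairs, if matched (8 pairs, nominal alpha 0.023).** The paired SE is 0.379 x sqrt(1 - rho) with 7 degrees of freedom.

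| rho | Type I error, unpaired test | Power at 1.38, unpaired | Power at 1.38, paired |
|---|---|---|---|
| 0 | 0.023 | 84.7% | 75.1% |
| 0.3 | 0.009 | 87.8% | 89.1% |
| 0.5 | 0.004 | 90.1% | 96.8% |

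At rho = 0.2 the paired power is 84.4%, still slightly under the plan's 84.7%. The crossover therefore lies at about 0.2 to 0.3. A random pair term that drops out when its estimated variance is zero keeps the power, but at rho = 0 its type I error is about 0.031 instead of 0.023.

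**The case against.** The strongest reply has four parts.

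- **The clustering is modelled.** Community, site and participant all have random effects, with time interactions. A reader might infer from the missing pair term that the standard error ignores the design. The documents do not support that. If pairs were formed within community, the community terms may also absorb some of what paired sites share.
- **Matched allocation is not documented.** A reader might take the word pair to mean one site per arm, but it could be a scheduling label. The only description of allocation is the coin-flip wording in section 7.1.
- **No false-positive risk follows from positively correlated pairs.** Leaving them out makes the test conservative. Type I error would rise only if paired sites were negatively correlated (0.036 at rho = -0.2).
- **Wave need not bias treatment.** It is tempting to say that because wave is tied to follow-up length, the treatment estimate is confounded. Primary inference is on treatment x time, and with balanced arms and a linear effect the bias is about zero. One site per arm in each pair would supply that balance.

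All four stand, and they limit the pair issue to a sensitivity analysis. They do not answer the wave issue. Balance within wave is not stated, linearity is not argued for, and section 8.1 is silent on the six-month-only data. Section 5.2 mentions an attached revised timeline that includes data analysis. It was not available for review and may address part of this.

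**Conclusion.** The point holds for wave in the Aim 1 model. Twelve-month SPPB is missing by wave, wave is not modelled, and one linear slope combines sites with different follow-up lengths. The size runs from about zero (arms balanced within wave, linear effect), through about 0.15 points/year (one-site imbalance, 0.8 points/year wave slope difference), to a 12-month estimate between 1.10 and 1.66 for a true 1.38 when the effect is non-linear. Wave 1 alone stays within 1.33 to 1.42. These sizes rest on assumed variances, an assumed five wave 1 pairs and an assumed slope difference, so they illustrate what could happen in this trial and do not estimate it.

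Wave terms remove the imbalance problem but not the non-linearity problem, which needs its own analysis. For pairs, the documents do not establish a fault. Whether adjustment helps depends on an unknown correlation, and pair should not be required in the primary model. The Aim 2 model also lacks wave and pair, but it works on one-year claims periods, not on the shortened assessment visits, and nothing was calculated for it.

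**What to change.** 1. In section 8.1, add wave and wave x time as fixed effects to the Aim 1 model. Cost: about one site-level degree of freedom, or 84.7% to 84.0% power at 1.38 under the original design.
2. State how the six-month-only and baseline-only wave 2 data enter the primary analysis.
3. Add a sensitivity analysis of the 12-month effect, using either visit-specific (categorical) time or wave 1 only. Cost: less precision than the pooled slope, because wave 2 then contributes little or nothing to the 12-month contrast.
4. State how pairs were formed and whether sites were randomized one per arm within pairs and within wave. If they were, report a pair-adjusted analysis with matching degrees of freedom as a sensitivity analysis and leave the primary model without pair.

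All four are changes of wording and analysis code. None needs new data.
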